7.1.5. Relationship of an Adverse Event to OCS Reduction

The relationship of an adverse event to OCS reduction (such as symptoms of adrenal insufficiency) will be indicated (yes/no) on the CRF.

7.1.6. Serious Adverse Events

7.1.6.1. Definition of a Serious Adverse Event

A serious adverse event is an adverse event occurring at any dose that results in any of the following outcomes or actions:

- death
- a life-threatening adverse event (ie, the patient was at immediate risk of death from the event as it occurred); does not include an event that, had it occurred in a more severe form, might have caused death
- inpatient hospitalization or prolongation of existing hospitalization, which means that hospital inpatient admission and/or prolongation of hospital stay were required for treatment of an adverse event, or that they occurred as a consequence of the event. Hospitalizations scheduled before study entry will not be considered serious adverse events, unless there was worsening of the preexisting condition during the patient's participation in this study. Note: Hospitalizations due to asthma exacerbation will be reported as serious adverse events if the presentation or outcome is more severe than the patient's known course of asthma
- persistent or significant disability or incapacity (refers to a substantial disruption of one's ability to conduct normal life functions)
- a congenital anomaly/birth defect
- an important medical event that may not result in death, be life-threatening, or require hospitalization but may jeopardize the patient and may require medical intervention to prevent one of the outcomes listed in this definition. Examples of such events are intensive treatment in an emergency room or at home for allergic bronchospasm; blood dyscrasias or convulsions that do not result in hospitalization; or the development of drug dependency or drug abuse. Note: Any suspected transmission of an infectious agent via a medicinal product is considered an important medical event

An adverse event that does not meet any of the criteria for seriousness listed above will be regarded as a nonserious adverse event.

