3.14. Stopping Rules and Discontinuation Criteria

Other than pregnancy, there are no formal rules for study drug discontinuation in this study. During the conduct of the study, serious adverse events and adverse events of special interest will be reviewed by the sponsor (see Section 7.1.6) as they are reported from the investigational center to identify safety concerns. The study may be terminated by the sponsor at any time for reasons including, but not limited to a safety concern.

A patient may discontinue participation in the study at any time for any reason (eg, lack of efficacy, consent withdrawn, adverse event).

The investigator and/or sponsor can withdraw a patient from the study for reasons including, but not limited to, a change in the medical condition or an adverse event that alters the patient's benefit/risk (eg, pregnancy, a related severe hypersensitivity reaction, or related severe myalgia/muscle event), a protocol violation or deviation as defined in Section 11.1.2, or noncompliance.

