7.1. Adverse Events

7.1.1. Definition of an Adverse Event

An adverse event is any untoward medical occurrence in a patient administered a pharmaceutical product, regardless of whether it has a causal relationship with this treatment.

In this study, any adverse event occurring after the clinical study patient has signed the ICF should be recorded and reported as an adverse event.

An adverse event can, therefore, be any unfavorable and unintended physical sign, symptom, or laboratory parameter that develops or worsens in severity during the course of this study, or significant worsening of the disease under study or of any concurrent disease, whether or not considered related to the study drug. Asthma exacerbation is an efficacy variable for this study and should be captured on the asthma exacerbation CRF; accordingly, asthma exacerbations should not be recorded as adverse events unless assessed as more severe than the patient's usual disease course. In this case, the investigator should determine if the adverse event is nonserious or serious based on seriousness criteria, as defined in Section 7.1.6. A new condition or the worsening of a pre-existing condition will be considered an adverse event. Stable chronic conditions (such as arthritis) that are present before study entry and do not worsen during this study will not be considered adverse events.

Accordingly, an adverse event can include any of the following:

- intercurrent illnesses
- physical injuries
- events possibly related to concomitant medication

- significant worsening (change in nature, severity, or frequency) of pre-existing conditions
- drug interactions
- laboratory or diagnostic test abnormalities that result in the withdrawal of the patient from the study, are associated with clinical signs and symptoms or a serious adverse event, require medical treatment or further diagnostic work-up, or are considered by the investigator to be clinically significant. (Note: Abnormal laboratory test results at the screening visit that preclude a patient from entering the study or receiving study treatment are not considered adverse events.)
- events associated to study procedure (eg, clinically significant adrenal insufficiency)

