7.1.8. Withdrawal Due to an Adverse Event

Any patient who experiences an adverse event may be withdrawn from the study or from study treatment at any time at the discretion of the investigator. If a patient is withdrawn wholly or in part because of an adverse event, both the adverse events page and termination page of the CRF will be completed at that time.

The patient will be monitored at the discretion of the investigator (eg, until the event has resolved or stabilized, until the patient is referred to the care of a health care professional, or until a determination of a cause unrelated to the study drug or study procedure is made). The investigator must inform the clinical project physician (CPP)/clinical leader as soon as possible of all patients who are being considered for withdrawal due to adverse events. Additional reports must be provided when requested.

If a patient is withdrawn from the study or study drug for multiple reasons that include adverse events, the termination page of the CRF should indicate that the withdrawal was related to an adverse event. An exception to this requirement will be the occurrence of an adverse event that, in the opinion of the investigator, is not severe enough to warrant discontinuation but requires the use of a prohibited medication, thereby requiring discontinuation of the patient. In such a case, the reason for discontinuation would be need to take a prohibited medication, not the adverse event.

If possible, a blood sample for measurement of serum reslizumab concentrations will be obtained from patients experiencing an adverse event leading to withdrawal, a serious adverse event, an

observation of any severe hypersensitivity reaction (eg, anaphylaxis), or an exacerbation of asthma symptoms.

Withdrawal from the study due to worsening of asthma or a CAE will be considered a withdrawal due to lack of effect, not a withdrawal due to an adverse event.

A patient should only be designated as lost to follow-up if the site is unable to establish contact with the subject after 3 documented attempts via 2 different methods (phone, text, e-mail, certified letter, etc).

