7.8. Methods and Timing of Assessing, Recording, and Analyzing Safety Data

All adverse events will be reviewed on a periodic basis by the CPP/medical monitor according to the safety monitoring plan (eg, scheduled safety reviews for reslizumab) as interim/preliminary safety databases become available. Safety data will additionally be evaluated periodically and ad hoc (if necessary) in the Product Safety Group.

Methods and timing of assessing safety data are discussed in Section 3.16. Procedures for recording safety data are discussed in Section 13.1 and methods of analyses are discussed in Section 9.7.

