6.3.3.2. Analysis

The annualized rate of CAEs will be analyzed using the generalized linear model (GLM) for data from the negative binomial distributions, commonly referred to as the negative binomial (NB) regression model. The NB model will include factors for treatment group, randomization strata (age and OCS dose as defined in Section 2.4), number of exacerbations in the previous year, and an offset variable. The offset variable will be calculated as the logarithm of follow-up duration minus the summed duration of exacerbations during the follow-up. Age and OCS dose will be based on data recorded in the clinical database.

The ratio of CAE rate between the treatment groups and its 95% CI will be estimated from the NB model. Treatment effect will be evaluated using the likelihood based chi-square test. The analysis of clinical asthma exacerbations will be on-treatment, excluding exacerbations observed after stopping study treatment. For patients who complete treatment, the treatment period will be defined from the first dose of study drug to the end of treatment (week 24) visit. For patients who prematurely discontinue treatment, the treatment period will be defined from the first dose of study drug to the last dose of study drug + 4 weeks. Analyses will only be performed if a sufficient number of patients have exacerbations for the model to converge satisfactorily.

The following sample SAS[®] code pertains to the analysis of CAEs.

```
proc genmod data=<<>>;
  class treatment strata1 strata2;
  model cae=treatment strata1 strata2 nexac /dist=negbin link=log offset=log_futime;
  estimate "CAE rate ratio" treatment 1 -1;
  lsmeans treatment /diff exp cl;
  ods output lsmeans=<<>>;
  ods output lsmeandiffs=<<>>;
run;
```

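### Asthma admissions judged to be the patient's known course bypass SAE reporting, the AE-based reviews as described and the AE/SAE tables, and are counted only inside composite efficacy endpoints

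*Protocol*

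**What the plan says.** **Objective.** Protocol 2.2.8 and SAP 1.8 include the safety of tapering OCS in the safety objective. The measures listed there are adverse events, laboratory tests, vital signs, ECG, physical examination, adrenal insufficiency and concomitant medication. Exacerbations and asthma admissions are not listed.

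**Classification.** Protocol 7.1.1 sends exacerbations to their own case report form as an efficacy variable and says that "asthma exacerbations should not be recorded as adverse events unless assessed as more severe than" what is usual for that patient. For admissions, Protocol 7.1.6.1 says: "Hospitalizations due to asthma exacerbation will be reported as serious adverse events if the presentation or outcome is more severe than" the patient's known asthma course. Protocol 7.1.8 adds: "Withdrawal from the study due to worsening of asthma or a CAE will be considered a withdrawal due to lack of effect", not to an adverse event.

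**Review during the study.** Protocol 3.14 says that "serious adverse events and adverse events of special interest will be reviewed by the sponsor". Protocol 7.8 says: "All adverse events will be reviewed on a periodic basis by the CPP/medical monitor according to the safety monitoring plan". It continues: "Safety data will additionally be evaluated periodically and ad hoc (if necessary) in the Product Safety Group".

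**Analysis.** SAP 6.3.3.1 defines a clinical asthma exacerbation (CAE) by any one of systemic corticosteroid use, an asthma admission or an asthma emergency visit. SAP 6.3.3.2 says: "The analysis of clinical asthma exacerbations will be on-treatment, excluding exacerbations observed after stopping study treatment". SAP Section 7 has no table of exacerbations, asthma admissions or emergency visits as such.

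**The concern.** The protocol lowers OCS, in both arms, in patients selected because they depend on it. An exacerbation that needs admission is a foreseeable result of such a taper. Whether it is treated as a safety event depends on how the investigator compares it with the patient's history, and the protocol gives no criterion or look-back period for that comparison. Two investigators could classify the same admission differently. In a population this severe, admission may be part of the known course for some patients, so the rule could exclude most events in those with the worst histories. That last step is an inference; the documents do not say it.

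Two things are at stake. The SAE table may understate how many patients were admitted for asthma during the taper. And a build-up of such admissions is not part of what the described in-study reviews are said to look at. The category is not marginal in this programme: Protocol 1.3.2.2 reports asthma as the SAE with the highest incidence in the earlier placebo-controlled asthma studies, with 24 patients (2%) on reslizumab 3 mg/kg and 24 (3%) on placebo.

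**Working it through.** The plan gives no admission figure, so there is none to reproduce. The check follows one event through the text: an asthma admission on treatment that the investigator regards as typical for the patient.

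1. **SAE or AE?** Neither, under Protocol 7.1.6.1 and 7.1.1. It goes on the exacerbation form.
2. **Expedited or special-interest event?** No. Protocol 7.1.7.2 names anaphylaxis, malignancy, opportunistic infection and helminth infection. SAP 7.3.1 does not list exacerbations.
3. **In-study review?** Protocol 3.14 is defined on SAEs and special-interest events, and the medical monitor's review in Protocol 7.8 on adverse events. The event is in neither. The Product Safety Group's material is called safety data without further definition, so inclusion is neither stated nor excluded. A data monitoring committee appears only in the abbreviation list.
4. **Withdrawal route?** If the patient leaves because of the event, Protocol 7.1.8 classes this as lack of effect. The duty in that section to inform the clinical project physician concerns withdrawals for adverse events.
5. **Safety tables?** SAP 7.3 tabulates recorded AEs and SAEs, so the event is absent. A steroid burst could show in the separate OCS summary of SAP 7.9.1, but not as an admission.
6. **Efficacy analyses?** The event counts in the annualized CAE rate (SAP 6.3.3.2), in time to first CAE (SAP 6.4.2.2) and, if it falls in weeks 20 to 24, in loss of control (SAP 6.2.1). Each uses the same composite. Days of corticosteroids for exacerbations (SAP 6.3.2.2.3) is not an admission count. The rate model is run only if enough patients have exacerbations for it to converge.
7. **After stopping drug?** For patients who stop early, the CAE window ends 4 weeks after the last dose. Protocol 4.5.1 keeps these patients in scheduled visits to week 24, so later events can be collected but fall outside that analysis. By contrast, SAP 7.3 gives post-treatment AEs their own summary.
8. **At follow-up?** Protocol 3.1.4.1 lists CAEs and related health care use at the visit 8 weeks after end of treatment. Table 5 marks that assessment only from visit 13 to visit 19, and Protocol 3.16.4 does not list it for visit 20. These passages conflict.

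**Size, as illustration only.** Let r be the share of patients with an asthma admission and f the share of those judged typical. Assume one admission per patient. Planned patients are 2 × 76 = 152. Patients missing from the SAE table = 152 × r × f. Both r and f are assumed.

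| r | Admitted (152 × r) | f = 25% | f = 50% | f = 75% |
|---|---|---|---|---|
| 2% | 3.04 | 0.76 | 1.52 | 2.28 |
| 3% | 4.56 | 1.14 | 2.28 | 3.42 |
| 5% | 7.6 | 1.9 | 3.8 | 5.7 |
| 10% | 15.2 | 3.8 | 7.6 | 11.4 |

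For any r, the SAE table shows the fraction 1 − f of admitted patients.

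**The case against.** A reader might infer that the main harm of the taper reaches no safety review and no safety table. The documents do not support that. Events judged worse than usual become AEs or SAEs. SAEs go to the sponsor within 24 hours (Protocol 7.1.6.3.1), are reviewed and are tabulated (SAP 7.3). AEs linked to OCS reduction are flagged (Protocol 7.1.5), and those linked to OCS withdrawal are summarized separately (SAP 7.3.1.7). SAP Section 7 is also not limited to AEs: it covers laboratory tests, vital signs, ECG, physical examination and medication. Calling exacerbations the main harm is a judgment; the documents do not rank harms.

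A reader might also infer that typical admissions cannot reach the medical monitor or the Product Safety Group. That goes too far. The Group's remit is not defined, and the safety monitoring plan cited in Protocol 7.8 is not among the documents. Protocol 7.1.10 requires contact with the medical monitor after a medical emergency. That section concerns protocol deviations, but its wording might cover some admissions.

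The events are also not lost. They are recorded and compared by arm as efficacy, so an imbalance between arms could show there. Some exploratory endpoints are redacted, and a separate analysis of health care use could be among them. Finally, the rule was deliberate: Amendment 02 gives clarification and alignment of reporting as its reasons.

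All of this narrows the point to admissions judged typical and to the visible text. It does not supply a safety table that counts them, or a statement that they are part of the periodic review.

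**Conclusion.** The narrow point holds. Followed as written, the SAE rule leaves typical-course asthma admissions out of SAE reporting, the AE-based reviews as described and the AE/SAE tables. In the visible text they are counted only within on-treatment composites that do not separate admissions. This sits poorly with a safety objective that names the taper.

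The size is unknown, because the documents give neither an admission rate nor the share judged typical. On the assumed ranges above, between about 0.8 and 11.4 of 152 patients would be missing from the SAE table. The asthma SAE percentages in Protocol 1.3.2.2 cannot settle this: they are SAE counts from other studies, not admission rates for this population.

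The SAE rule does not change the primary analysis or the CAE endpoint. The point concerns how completely the safety section and the ongoing review show one serious outcome, and it is worth correcting because the correction is cheap.

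**What to change.** 1. In SAP Section 7, add a table by arm, on the safety analysis set, of patients and events with an asthma-specific hospital admission or emergency visit, regardless of AE or SAE status. Show on-treatment events and, separately, events after stopping study drug for as long as they are collected.
2. In Protocol 7.8, state that a blinded listing of these events from the exacerbation form is part of the data that the medical monitor and the Product Safety Group already review periodically.
3. Reconcile Protocol 3.1.4.1 with Table 5 and Protocol 3.16.4 on whether CAEs and related health care use are assessed at the 8-week follow-up visit, and carry the result into SAP 2.1.4.1 and SAP Table 4. This decides whether the table can include follow-up events.

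Expedited SAE reporting, the CAE endpoint and clinical management stay unchanged. The cost is one table, one blinded listing and short wording changes. On-study events come from data already collected on the exacerbation form; follow-up events depend on item 3.

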7.1.6.2. Expectedness

A serious adverse event that is not included in the Adverse Reaction section of the relevant reference safety information by its specificity, severity, outcome, or frequency is considered an unexpected adverse event. The reference safety information for this study is the IB. The sponsor's Pharmacovigilance Department will determine the expectedness for all serious adverse events.

7.1.6.3. Reporting a Serious Adverse Event

7.1.6.3.1. Investigator Responsibility

To satisfy regulatory requirements, all serious adverse events (as described in Section 7.1.6.1) (including the protocol-defined follow-up period, described in Section 7.1.2), regardless of

judged relationship to treatment with the study drug, must be reported to the sponsor by the investigator within 24 hours of when the investigator learns about it. Completing the serious adverse event form and reporting the event must not be delayed, even if not all the information is available. The investigator does not need to actively monitor subjects for adverse events once the study has ended. Serious adverse events occurring to a patient after the study should be reported to the sponsor if the investigator becomes aware of them.

The serious adverse event form should be sent to the local safety officer (LSO) or other designated personnel (a contract research organization [CRO] in a country without a sponsor LSO) (contact information is in the Clinical Study Personnel Contact Information section); the LSO will forward the report to the sponsor's Global Patient Safety & Pharmacovigilance Department.

The following information should be provided to record the event accurately and completely:

- study number
- investigator and investigational center identification
- patient number
- patient initials
- onset date and description of adverse event
- investigator's assessment of the relationship of the adverse event to the study drug (no reasonable possibility, reasonable possibility)

Additional information may include the following:

- age and sex of patient
- date of first dose of study drug
- date and amount of last administered dose of study drug
- action taken
- outcome, if known
- severity
- concomitant therapy (including doses, routes, and regimens) and treatment of the event
- pertinent laboratory or other diagnostic test data
- medical history
- results of dechallenge/rechallenge, if known
- for an adverse event resulting in death:
 - cause of death (whether or not the death was related to study drug as determined by the investigator)
 - autopsy findings (if available)

Each report of a serious adverse event will be reviewed and evaluated by the investigator and the sponsor to assess the nature of the event and the relationship of the event to the study drug, study procedures, and to underlying disease. The sponsor will also evaluate the expectedness of all serious adverse events.

Additional information (follow-up) about any serious adverse event unavailable at the initial reporting should be forwarded by the investigational center within 24 hours of when it becomes known to the same address as the initial report.

For all countries, the sponsor's Global Patient Safety & Pharmacovigilance Department will distribute the Council for International Organizations of Medical Sciences form/XML file to the LSO/CRO for local submission to the regulatory authorities, IEC/IRBs, and investigators, according to regulations. The investigator is responsible for ensuring that the IRB/EC is also informed of the event, in accordance with local regulations.

Blinding will be maintained for the people who are involved directly in the study. Therefore, in case of a SUSAR, only the LSO/CRO will receive from pharmacovigilance the unblinded report for regulatory submission; the others will receive a blinded report.

Note: Although pregnancy is not a serious adverse event, the process for reporting a pregnancy is the same as that for reporting a serious adverse event, but using the pregnancy form (see Section 7.2).

If possible, a blood sample for measurement of serum reslizumab concentrations will be obtained from patients experiencing a serious adverse event, an adverse event leading to withdrawal, an observation of any severe hypersensitivity reaction (eg, anaphylaxis), or an exacerbation of asthma symptoms.

